4.4 Definition of Phases, Visit, or Windows

Visit labels will be used for reporting. For listings ordered by assessment date, if unscheduled visits are associated with a date of assessment, these will be included in the listing by date with the visit described as ‘unscheduled.’ Otherwise, if no date of assessment is associated with the unscheduled visit data, listings will be ordered by visit with unscheduled visits presented last. Unscheduled visits associated with discharge from hospital will be used in lieu of Day 8 in participants for whom there is no Day 8 assessment, and other unscheduled visits will not be reported in summaries.

Visits will be displayed as follows:

Visit Label	Short Descriptor if needed to accommodate space restrictions
Screen	SCRN
Baseline	BSLN
Day 2 (24h post-dose)	D2
Day 3	D3
Day 5	D5
Day 8	D8
Day 10	D10
Day 30	D30
Unscheduled	UNSCH

4.5 Display of Treatment Groups

Summaries will be displayed by treatment group. Summaries and listings based on the Safety population will be displayed by actual treatment received.

Treatment groups will be displayed as follows with respect to labels and ordering.

Label	Short Label if needed to accommodate space	Definition
All Heparin	All HEP	Prophylactic and therapeutic doses heparin groups combined
Heparin Prophylactic	HEP Pro	Initial Heparin Dosing Strategy (Prophylactic Heparin) as recorded by the investigator in the Case Report Form (CRF)
Heparin Therapeutic	HEP Ther	Initial Heparin Dosing Strategy (Therapeutic Heparin) as recorded by the investigator in the CRF
rNAPc2 Lower		Lower Dose rNAPc2 (5 µg/kg on Day 1 followed by 3µg/kg on Days 3 and 5)
rNAPc2 Higher		Higher Dose rNAPc2 (7.5 µg/kg on Day 1 followed by 5µg/kg on Days 3 and 5)
ALL rNAPc2		Lower and Higher rNAPc2 doses combined
Overall		All participants who receive any study treatment (Heparin or rNAPc2)

4.6 Protocol Deviations or Violations

All protocol deviations will be collected in the clinical trial management system (CTMS) database. Major deviations will be identified manually and programmatically prior to unblinding. A summary of major protocol deviations will be given by frequency tables showing the number of participants with major protocol deviations overall and by deviation. Protocol deviations will be listed for all screened participants.

5 Statistical Methods

5.1 Missing Data

The primary analysis will be performed using all complete data and, for subjects who do not have completed primary endpoint data, values obtained in the ± 48-hour window around Day 8 or Day of Discharge, as described in [Section 7.1.1](#), will be used. If no values are present from the ± 48-hour window, Last Observation Carried Forward (LOCF) will be used. All values measured after the administration of the final dose will be eligible for LOCF.

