8 STUDY ASSESSMENTS AND PROCEDURES

8.1 STUDY PROCEDURES

8.1.1 SCHEDULE OF ACTIVITIES

Table 2a. Schedule of Activities (SoA)

Activity	Screen Day -7 to 1	Baseline Day 1	Day 2 (24h post-dose \pm 2h)	Day 3 \pm 1d	Day 5 \pm 1d	Day 8 \pm 1d	Day of Hospital Discharge	Day 30 \pm 3d
Informed consent	x							
Assess eligibility	x	x						
Randomize		x						
Medical history (COVID-19, cardiovascular, medical/ surgical history) ^b		x						
Concomitant medication ^b		x	x	x	x	x	x	x ^d
Baseline demographics ^b	x							
Focused physical examination, vital signs, weight, height ^b		x						
Study medication ^c		rNAPc2 7.5 μ g/kg SC on Day 1 and 5 μ g/kg SC on Days 3 and 5 or rNAPc2 5 μ g/kg SC on Day 1 and 3 μ g/kg SC on Days 3 and 5 or heparin per SoC						
Local laboratory values	x ^a	Record values of interest performed in the hospital clinical laboratory until hospital discharge or day 30 visit (whichever is first). In the case where a lab test is measured multiple times per day, the first scheduled values as well as any additional values that represent a clinically significant change should be reported.						
Assess need for inpatient medical services & complete ACTT			Daily until discharged to outpatient status or death or Day 30 reached					
Clinical & adverse events ^g	x	x	x	x	x	x	x	x ^d
Post-COVID functional status (PCFS) scale							x ^h	x ^d
Vital status								x ^d
Healthcare utilization							x	x ^d
Central Laboratory assessments (see Table 2b)		x	x	x ^e		x ^f	x ^f	x ^e

^a Local lab D-dimer drawn during hospitalization and prior to randomization will be used for eligibility and randomization stratification

^b May be obtained/extracted from medical record to minimize staff exposure to COVID-19

^c rNAPc2 must be dosed on Days 1, 3 and 5; only one rNAPc2 dose regimen is anticipated in Phase 3; Participants randomized to receive heparin will have doses administered per standard of care (SoC)

^d Participants who are discharged prior to Day 30 may have these activities performed remotely

^e For phase 2b only

^f If participant is discharged prior to Day 8, central laboratory assessments should be performed at hospital discharge

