The following procedures will occur during the Day 5 visit:

- Concomitant medication (may be obtained/extracted from the medical record to minimize staff exposure to COVID-19)
- Study medication administration
 - If an rNAPc2-allocated participant is discharged from the hospital before receiving the Day 5 dose, the dose(s) should be recorded in the electronic Case Report Form (eCRF) as not administered.
- Local laboratory values, if applicable
- Assess the need for inpatient medical services and complete ACTT
 - The need for inpatient medical services should be assessed daily after randomization until the participant is discharged from the hospital, deceased, or Day 30 visit is reached.
 - Documentation pertaining to this assessment must be provided to the CEC as outlined in the Site Manual.
- Clinical events and adverse events assessment
 - Assess for the occurrence of any adverse events and report via the eCRF as appropriate. See [Section 8.4 Adverse Events and Serious Adverse Events](#) for more information about adverse events.
 - Assess for the occurrence of any clinical event that suggests the possibility that an efficacy outcome event has occurred. See [Section 8.2 Efficacy Assessments](#) for more information about clinical events of interest.

Day 8 Visit (+/- 1 Day)

The following procedures will occur during the Day 8 visit:

- Concomitant medication (may be obtained/extracted from the medical record to minimize staff exposure to COVID-19)
- Study medication administration, if randomized to heparin and still hospitalized
- Local laboratory values, if applicable
- Assess need for inpatient medical services and complete ACTT
 - The need for inpatient medical services should be assessed daily after randomization until the participant is discharged from the hospital, deceased, or Day 30 visit is reached.
 - Documentation pertaining to this assessment must be provided to the CEC as outlined in the Site Manual.
- Clinical events and adverse events assessment
 - Assess for the occurrence of any adverse events and report via the eCRF as appropriate. See [Section 8.4 Adverse Events and Serious Adverse Events](#) for more information about adverse events.
 - Assess for the occurrence of any clinical event that suggests the possibility that an efficacy outcome event has occurred. See [Section 8.2 Efficacy Assessments](#) for more information about clinical events of interest.

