2.5 Secondary Endpoints

2.5.1 Efficacy

Secondary efficacy endpoints are:

- Change in D-dimer level from baseline to 24 hrs post the institution of study medication following randomization (Study Day 2), and 48 hours after institution of study medication (Study Day 3)
- Probability of discharge as assessed by ACTT ≥ 6 by Day 8 and Day 30 post randomization
- Composite of death, thrombosis, organ support, or rehospitalization within 30 days adjudicated as to its relatedness to COVID-19
- Change in biomarkers associated with outcomes including those related to coagulation and inflammation from baseline through Day 8

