5.2 Analysis Populations and Scopes

All analyses are based on 2 elements:

- Analysis population, which specifies which participants will be included in an analysis; and
- Data scope, which specifies the time window within which data will be included in an analysis

Five analysis populations are defined for this study.

The **Intent-to-Treat (ITT) population** will include all participants who are randomized. Participants will be analyzed according to the treatment group allocated by randomization.

The **modified Intent-to-Treat (mITT) population** will include all participants who are randomized and received at least one dose of study drug. Participants will be analyzed according to the treatment group allocated by randomization.

The **Per Protocol population** will include all participants who are randomized, receive all three doses of study drug post randomization or receive SoC drug through day 7, have no major deviations from the protocol that affect the primary endpoint, and complete all pre-specified study assessments/activities. Participants will be analyzed according to the treatment actually received.

The **Safety population** will include all participants who are randomized and receive at least one dose or part of a dose of study treatment post-randomization. Participants will be analyzed according to the treatment actually received.

The **All Screened population** will be defined as all participants with any data entered into the database.

The analysis populations will be listed by participant.

The ITT, mITT and Per Protocol data scope includes outcomes and events observed from a given participant’s date of randomization until either their final or Day 30 contact, determined by whichever occurs first. This will be applied mainly to the analyses of efficacy endpoints.

The ITT, mITT and Per Protocol data scope will also be used for the secondary safety endpoints of major or non-major clinically relevant bleeding through Day 30 and any bleeding through Day 30.

The on-treatment data scope will include all outcomes and events observed from randomization until 72 hours following permanent discontinuation of the study drug. This on-treatment data scope will be applied mainly to the analyses of safety endpoints.

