7.1.1 Primary Analysis of the Primary Efficacy Endpoint

Proportional change, represented by percent change, will be calculated as $100 \times (\text{D-Dimer level at Day 8 or Day of Discharge if prior to Day 8} - \text{D-Dimer level at baseline}) / \text{D-Dimer level at baseline}$ and will be based on data provided by the central laboratory, or local laboratory paired samples if the central laboratory values are not available. The pairing process will be operationalized as outlined:

For Day 1 (baseline) paired local-local or central-central laboratory values:

1. Use any lab D-dimer drawn during the current admission and up to randomization

2. Use the laboratory sample closest to randomization if there are multiple D-dimer measurements.
3. All samples obtained more than 1-hour post-initiation of study drug are ineligible.

For Day 8 or Day of Discharge paired laboratory values:

1. Use laboratory samples collected within ± 48 h of the Day 8 or Day of Discharge study visit (whichever occurs first).
2. If there are multiple laboratory samples collected within that window, use the lab value on the target day; if not available, use the lab value immediately after the target visit day.

A Wilcoxon rank sum test will be used to compare proportional change from baseline to Day 8, or Day of Discharge if prior to Day 8, between treatment groups. The between treatment group rank sum test is considered the primary analysis of the primary endpoint.

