11.2 Primary Efficacy Endpoint Subgroup Analyses

In order to test for subgroup sensitivities, a Bayesian generalized linear mixed effects model will be constructed. This model will evaluate the influence of pre-specified subgroups of interest, D-dimer stratum, and potential site-level heterogeneity in patient outcomes.

A separate set of analyses for each rNAP2 dosing instance will be constructed, such that the effect on D-dimer of each incremental dose of rNAP2 is estimated. These analyses will therefore be equivalent in

formulation to the Primary Efficacy Analysis as specified above, with estimates of instantaneous treatment effect at Days 3, 5, and 8 for subjects receiving 1, 2 or 3 doses of rNAPc2 or receiving SoC heparin through days 1, 3, and 7, respectively.

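### SAP 5.1 ties last-observation-carried-forward in the primary analysis to an undefined final dose, so the same early D-dimer can qualify in one arm and not in the other; the reach is narrow and the fix cheap

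*SAP*

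**What the plan says.** SAP 5.1 sets an order for the primary analysis: the complete endpoint value, then a value within 48 hours of the target day, then last observation carried forward (LOCF). The one condition on the last step is "All values measured after the administration of the final dose will be eligible for LOCF". SAP 7.1.1 centres the window on the "Day 8 or Day of Discharge study visit (whichever occurs first"), which for Day 8 is about Days 6–10. The same section makes the between-group Wilcoxon rank sum test, pooled rNAPc2 against heparin, the primary analysis.

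The dosing schedules differ. Protocol 8.1.1 fixes rNAPc2 on Days 1, 3 and 5. For the control arm it says "Participants randomized to receive heparin will have doses administered per standard of care (SoC"). The Day 8 and Day 30 visits in Protocol 8.1.3 still list "Study medication administration, if randomized to heparin and still hospitalized".

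Two SAP passages set the courses side by side, neither of them for LOCF. The Per Protocol definition in SAP 5.2 asks that participants "receive all three doses of study drug post randomization or receive SoC drug through day 7". SAP 11.2 matches one, two or three rNAPc2 doses with "receiving SoC heparin through days 1, 3, and 7, respectively".

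Central D-dimer is drawn in both arms on Day 1, Day 2, Day 3 and Day 8. For early discharge, Protocol 8.1.1 adds: "If participant is discharged prior to Day 8, central laboratory assessments should be performed at hospital discharge".

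**The concern.** A carry-forward rule decides who enters the primary test and with what value. It should not depend on the treatment assigned. Here one phrase covers a three-dose course and an open-ended course that may run past Day 8. The natural reading is that values before the final dose do not qualify, although SAP 5.1 does not say so outright. On that reading, the arm with the later last dose loses values that the other arm keeps.

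If participants without a window value differ from the rest, keeping more of them in one arm biases the comparison. Without a definition, the choice also falls to whoever programs the analysis, in a trial where sites know the assignment.

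**Working it through.** **1. Eligibility under each reading, when no value lies in the window**

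| Participant | Last dose received | Scheduled course end (Day 5 rNAPc2, Day 7 heparin) |
|---|---|---|
| rNAPc2, stopped after Day 1 | Day 2 and Day 3 values eligible | no final dose reached |
| rNAPc2, stopped after Day 3 | Day 2 not eligible; Day 3 only if drawn after the dose (order not stated) | no final dose reached |
| rNAPc2, all three doses | only values after the Day 5 dose | only values after the Day 5 dose |
| Heparin, daily to Day 4 | Day 2 and Day 3 not eligible | no final dose reached |
| Heparin, daily to Day 7 or later | nothing before the window | nothing before the window |
| Heparin, stopped on Day 1 | Day 2 and Day 3 values eligible | no final dose reached |

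Daily heparin is an assumption; the protocol leaves the regimen to local practice. The last row shows that the difference comes from the dosing schedules rather than from the arm label. The second reading reduces the asymmetry but does not remove it: a late Day 5 value counts for rNAPc2 and not for heparin. No central draw is scheduled between Day 3 and the window, so that value would have to be a local one with a local baseline to pair.

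**2. Who reaches this step**

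- Discharge on Days 2–5: the window of discharge day ± 2 contains a scheduled Day 2 or Day 3 draw (for Day 5 it covers Days 3–7). LOCF is not needed if that draw was taken.
- Discharge on Days 6–7: the windows are Days 4–8 and 5–9, which hold neither draw, but a central sample is due at discharge.
- Study drug stopped early: Protocol 7.1 keeps assessments going, so a Day 8 sample is still due.
- What remains is mainly deaths before Day 6 and inpatients with no D-dimer on Days 6–10. Protocol 5.2 excludes patients expected to live less than 72 hours.

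The plan's 20% (0.20 × 80 = 16 per pooled arm) is the share lacking a Day 8 D-dimer, including early recovery. It is an upper bound on this group.

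**3. Illustration of size**

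The plan states no figure for this point. The following are assumptions: the number of carried values, and how far they are shifted. The model is a rank sum test (two-sided 0.05) on standard normal log change, with *n* observed per arm plus carried values shifted by 1 SD unless stated. The effect is set at 0.577 SD, which reproduces the plan's 88.3% power for a 30% reduction at 64 per arm. Nominal false rNAPc2 superiority is 2.5%. Power is for carried values worse than the rest, against power with none carried.

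| Observed per arm | Carried, rNAPc2 vs heparin | Two-sided error | False superiority, carried worse / better | Power |
|---|---|---|---|---|
| 76 (80 − 4) | 2 vs 0 | 5.0–5.1% | 1.7% / 3.3% | 91% vs 93% |
| 76 | 2 vs 1 | 4.9% | 2.0% / 2.8% | 92% vs 93% |
| 64 (80 − 16) | 2 vs 0 | 5.1% | 1.7% / 3.5% | 85% vs 88% |
| 64, shift 0.5 SD | 2 vs 0 | 5.0–5.1% | 2.0% / 3.0% | 87% vs 88% |
| 72 (80 − 8) | 4 vs 0 | 5.7–5.8% | 1.2% / 4.5% | 87% vs 92% |
| 64 | 8 vs 0 (extreme) | about 8.4% | 0.4% / 7.9% | 74% vs 88% |

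A single carried value (76 observed, 1 vs 0) gives 5.0% error and 92% power against 93%. With no shift there is no bias.

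A second model treats carried values as early measurements (log SD 0.4, against 0.9 at Day 8; also assumed). With 4 of 16 carried in rNAPc2 and none in heparin, two-sided error is 4.8–6.2%.

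**The case against.** The strongest reply is that the wording favours a scheduled-dose reading. Where the SAP means the end of actual treatment, as in the on-treatment scope of SAP 5.2, it speaks of permanent discontinuation. On a scheduled reading, Day 2 and Day 3 values are out in both arms and LOCF is nearly empty. This is a fair reading, but the SAP does not state it. It also gives no end of course for heparin under LOCF, and it still leaves the late Day 5 difference.

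The second reply concerns reach. To be carried in rNAPc2 only, a scheduled central value needs dosing stopped after Day 1 (or after Day 3 with a favourable draw order), no D-dimer in a five-day window, and no rescue by the discharge window or discharge sample. This stands, and it is why the point is low priority. The objection to the simulation stands too: the first model draws a Day-8-like value and adds a shift, and the counts are invented.

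A reader might infer from the extreme rows that the rule inflates type I error or favours rNAPc2. The documents do not support that. Nothing in them suggests 4 or 8 one-sided carried values. The rows that raise false superiority need carried participants to do better than the rest, whereas those who reach this step are mainly early deaths and continuing inpatients; most early recoverers are caught by the window. If the carried values are worse, false superiority falls below 2.5% and the cost is power.

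Multiple imputation (SAP 11.1) is a planned check in the ITT, mITT and Per Protocol populations, and Phase 3 excludes these data from its primary analysis. Both limit the consequences. Neither settles the primary rule.

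**Conclusion.** The point holds in a limited form. The condition in SAP 5.1 is undefined and makes entry into the primary rank sum test depend on arm-specific dosing. It does so clearly if the final dose is the last one received, and slightly if course ends of Day 5 and Day 7 are borrowed.

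The number affected and the size and direction of any bias cannot be derived from the documents. Under the assumptions above, one or two values carried in one arm only leave two-sided error near 5% and cost about 1–3 points of power. Larger effects need counts that the documents do not support. This is a cheap improvement to the primary rule, not evidence that the primary result would be wrong.

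**What to change.** Before unblinding, replace the final-dose condition in SAP 5.1 with one study-day cut-off, the same in both arms whatever the dose timing. For example, carry the last D-dimer from Day 5 onward. This keeps the apparent intent of using only values close to Day 8. Defining the final dose separately for each arm would settle the wording but keep the asymmetry. Report the participants carried forward and those excluded, by arm.

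The cost is one SAP sentence and minor reprogramming, with no new data. The downside is that a few participants with only earlier values stay out of the primary test. A Day 3 cut-off would keep more of them but carry values up to five days from Day 8 (8 − 3 = 5). The planned multiple imputation remains the check either way.

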5.1.1 Missing Values

In cases where data are missing but an entry is expected (e.g., required study procedure not performed) numeric values will appear in the database as follows:

- ‘Unable to obtain’ response will be recorded in the database as a ‘-97’.
- ‘Not Known’ response will be recorded in the database as a ‘-98’.

- ‘Not Applicable’ response will be recorded in the database as a ‘-99’ value.

These will be translated to meaningful entries during listing and/or summarization of the data as appropriate.

5.1.2 Undetectable Values

If a measured value of D-dimer is reported from the central laboratory as below the detectible limit of the assay, the value will be entered as 1 unit below the detectible limit. For example, if the result is ‘< 120 ng/mL’ the value will be entered as 119 ng/mL.

5.2 Analysis Populations and Scopes

All analyses are based on 2 elements:

- Analysis population, which specifies which participants will be included in an analysis; and
- Data scope, which specifies the time window within which data will be included in an analysis

Five analysis populations are defined for this study.

The **Intent-to-Treat (ITT) population** will include all participants who are randomized. Participants will be analyzed according to the treatment group allocated by randomization.

The **modified Intent-to-Treat (mITT) population** will include all participants who are randomized and received at least one dose of study drug. Participants will be analyzed according to the treatment group allocated by randomization.

The **Per Protocol population** will include all participants who are randomized, receive all three doses of study drug post randomization or receive SoC drug through day 7, have no major deviations from the protocol that affect the primary endpoint, and complete all pre-specified study assessments/activities. Participants will be analyzed according to the treatment actually received.

The **Safety population** will include all participants who are randomized and receive at least one dose or part of a dose of study treatment post-randomization. Participants will be analyzed according to the treatment actually received.

The **All Screened population** will be defined as all participants with any data entered into the database.

The analysis populations will be listed by participant.

The ITT, mITT and Per Protocol data scope includes outcomes and events observed from a given participant’s date of randomization until either their final or Day 30 contact, determined by whichever occurs first. This will be applied mainly to the analyses of efficacy endpoints.

The ITT, mITT and Per Protocol data scope will also be used for the secondary safety endpoints of major or non-major clinically relevant bleeding through Day 30 and any bleeding through Day 30.

The on-treatment data scope will include all outcomes and events observed from randomization until 72 hours following permanent discontinuation of the study drug. This on-treatment data scope will be applied mainly to the analyses of safety endpoints.

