6.4 STUDY INTERVENTION COMPLIANCE

Both rNAPc2 and heparin should be administered and documented in-hospital by hospital staff. Dates, doses and mode of administration will be recorded in the electronic Case Report Form (eCRF).

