The following procedures will occur during the Day 2 visit:

- Central laboratory samples must be collected 24h after the first dose of study drug (+/- 2hours)
- Concomitant medication (may be obtained/extracted from the medical record to minimize staff exposure to COVID-19)
- Assess need for inpatient medical services and complete ACTT
 - The need for inpatient medical services should be assessed daily after randomization until the participant is discharged from the hospital, deceased, or Day 30 visit is reached.
 - Documentation pertaining to this assessment must be provided to the CEC as outlined in the Site Manual.
- Clinical events and adverse events assessment
 - Assess for the occurrence of any adverse events and report via the eCRF as appropriate. See [Section 8.4 Adverse Events and Serious Adverse Events](#) for more information about adverse events.
 - Assess for the occurrence of any clinical event that suggests the possibility that an efficacy outcome event has occurred. See [Section 8.2 Efficacy Assessments](#) for more information about clinical events of interest.

Day 3 Visit (+/- 1 Day)

The following procedures will occur during the Day 3 visit:

- Concomitant medication (may be obtained/extracted from the medical record to minimize staff exposure to COVID-19)
- Study medication administration
 - If an rNAPc2-allocated participant is discharged from the hospital before receiving the Day 3 dose, the dose(s) should be recorded in the electronic Case Report Form (eCRF) as not administered.
- Local laboratory values, if applicable

- Assess need for inpatient medical services and complete ACTT
 - The need for inpatient medical services should be assessed daily after randomization until the participant is discharged from the hospital, deceased, or Day 30 visit is reached.
 - Documentation pertaining to this assessment must be provided to the CEC as outlined in the Site Manual.
- Clinical events and adverse events assessment
 - Assess for the occurrence of any adverse events and report via the eCRF as appropriate. See [Section 8.4 Adverse Events and Serious Adverse Events](#) for more information about adverse events.
 - Assess for the occurrence of any clinical event that suggests the possibility that an efficacy outcome event has occurred. See [Section 8.2 Efficacy Assessments](#) for more information about clinical events of interest.
- Central laboratory samples (Phase 2b only)

Day 5 Visit (+/- 1 Day)

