9.3 POPULATIONS FOR ANALYSES

Randomized participants consist of all screened participants with randomization assignment, regardless of whether or not study intervention was administered. Participants treated without being randomized or treated before randomization will not be considered as randomized and will not be included in any analysis population. The safety experience of these participants will be reported separately, and they will not be included in the safety population.

The efficacy analysis population will be the intent-to-treat (ITT) population, consisting of all randomized participants as defined above. Participants in the ITT population will be analyzed according to the treatment group allocated by randomization.

An additional efficacy analysis population for sensitivity analyses of the primary efficacy endpoints will be the modified intent-to-treat (mITT) population, consisting of the subset of the ITT population that received at least one dose of study drug. Participants in the mITT population will be analyzed according to the treatment group allocated by randomization.

A per protocol population will include all participants who are randomized and receive all three doses of study drug post-randomization. Participants will be analyzed according to the treatment actually received.

The safety analysis population will be the safety population, consisting of the randomized population who received at least one dose or part of a dose of study treatment. Participants will be analyzed according to the treatment received (rNAPc2 or heparin).

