8.3 Laboratory Data

A summary of laboratory (Central Laboratory) values (e.g., AST, ALT and bilirubin) outside normal limits (i.e., either above the ULN or below the lower limit of normal (LLN) where limits are defined), as well as a summary of any participant potentially meeting the criteria for Hy's law will be provided where Hy's Law criteria will be defined as: AST or ALT > 3× ULN and total bilirubin > 2× ULN at any time during the study.

9 Interim Analyses

Additional details of these analyses will be described in the DSMC Charter.

10 Composite and Net Endpoints

Composite endpoints will first be analyzed as an aggregate and then component-wise, as discussed in the context of modeling clinical events in [Section 7.2.3](#). The primary approach to net outcomes will be to perform them in all randomized patients in the 30-day study period.

Composite/net clinical outcomes include the combination of irreversible harm and efficacy outcomes, including:

- All-cause mortality, thrombotic events, initiation of organ support, rehospitalization adjudicated as to its relatedness to COVID-19.

11 Subgroup and Sensitivity Analyses

The sensitivity analyses will be performed on the ITT, mITT, and Per Protocol populations.

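### The Per Protocol rule ends treatment on different days in the two arms (third rNAPc2 dose, nominally Day 5; heparin through Day 7), so evaluable patients discharged on about Days 5-6 can count for rNAPc2 but not for heparin

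*SAP*

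**What the plan says.** SAP 5.2 sets the Per Protocol treatment criterion by arm: participants must "receive all three doses of study drug post randomization or receive SoC drug through day 7". They must also have no major deviation affecting the primary endpoint and must "complete all pre-specified study assessments/activities"; these two conditions are the same in both arms. Discharge is not mentioned.

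The protocol fixes the calendar behind this. The footnote to the Schedule of Activities (8.1.1) says "rNAPc2 must be dosed on Days 1, 3 and 5", and the Day 5 visit has a window of one day either side, so the third dose can fall on Days 4-6. Section 6.4 says "Both rNAPc2 and heparin should be administered and documented in-hospital by hospital staff", and the Day 8 visit in 8.1.3 lists heparin as study medication only for participants who are still inpatients.

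Protocol 9.3 words the population differently: "A per protocol population will include all participants who are randomized and receive all three doses of study drug post-randomization". It has no heparin criterion. Under protocol 9.4.1 the SAP governs where the two differ.

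The set is used in SAP Section 11: "The sensitivity analyses will be performed on the ITT, mITT, and Per Protocol populations".

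**The concern.** A Per Protocol set should apply the same test of adherence to both arms. Here an rNAPc2 participant meets the treatment criterion once the third dose is given, while a heparin participant must remain on treatment two nominal days longer. Between those two points, discharge decides who counts, and it does so in one arm only.

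Discharge day is a post-randomization outcome. SAP 2.5.1 makes the probability of discharge by Day 8 a secondary efficacy endpoint. The affected patients are not unevaluable: for anyone discharged before Day 8, both documents use the day-of-discharge D-dimer. Participants with valid endpoint data are therefore kept in one arm and dropped from the other, and the two Per Protocol groups are no longer comparable even if treatment does nothing. A sensitivity analysis with this feature cannot reliably support or question the ITT result.

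**Working it through.** The plan states no figure that depends on this rule, so there is nothing to reproduce. The check has two parts.

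**1. Eligibility by discharge day.** Inputs: third dose on nominal Day 5 (protocol 8.1.1); heparin through Day 7 (SAP 5.2); both treatments given in hospital (protocol 6.4 and 8.1.3).

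| Discharge day | rNAPc2 meets criterion | Heparin meets criterion |
|---|---|---|
| 3 or 4 | no | no |
| 5 (after the dose) or 6 | yes | no |
| 7 or later | yes | yes |

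The visit window blurs the edges. With a third dose on Day 4, an rNAPc2 participant discharged that day could qualify; one who leaves on Day 5 before dosing does not. Protocol 8.1.3 covers the latter case ("If an rNAPc2-allocated participant is discharged from the hospital before receiving the Day 5 dose") by recording the dose as not given.

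The common conditions do not close the gap. They apply to both arms, the discharge sample replaces the Day 8 sample, and other activities after discharge may be done remotely.

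**2. Possible size.** From the documents: 160 randomized 1:1:2, so 80 pooled rNAPc2 and 80 heparin; 20% unevaluable, so 160 × 0.8 / 2 = 64 per arm; Wilcoxon rank sum test, two-sided 5%. Not in the documents, hence assumed: the share q discharged in the gap (10%, 20%, 30%), an SD of 0.8 for the log D-dimer ratio, and a shift s in that log ratio for those patients.

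Numbers: of 80 per arm, this clause alone keeps 80 rNAPc2 and 80 × (1 − q) = 72, 64 or 56 heparin participants.

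Bias: with no treatment effect, the rNAPc2 mean log ratio is q × s and the heparin mean, after exclusion, is 0. The spurious geometric-mean ratio is exp(q × s); for example exp(0.2 × −0.6) = 0.89.

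Spurious ratio, with simulated two-sided rejection under no effect (4,000 runs per cell, 64 per arm before exclusion):

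| q | s = −0.6 (0.75 SD better) | s = −0.3 (0.375 SD better) | s = 0 | s = +0.3 (0.375 SD worse) |
|---|---|---|---|---|
| 10% | 0.94; 6.1% | 0.97; 5.2% | 1.00; 4.8% | 1.03; 5.4% |
| 20% | 0.89; 11.8% | 0.94; 6.2% | 1.00; 4.6% | 1.06; 6.7% |
| 30% | 0.84; 19.3% | 0.91; 8.4% | 1.00; 4.7% | 1.09; 8.0% |

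Runs set directly in SD units (6,000 per setting, early leavers better) gave 5.1% at 10% and 0.3 SD; 8.2% at 20% and 0.5 SD, of which 7.4% favoured rNAPc2; 12.2% at 20% and 0.8 SD; and 20.6% at 30% and 0.8 SD. A repeat with 4,000 runs gave 5.1%, 8.4%, 11.8% and 22%. Dropping the same discharge days from both arms returned every setting to about 5%.

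**The case against.** Five points can be made for the plan.

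- **The fastest recoverers are treated alike.** A reader might infer that the rule removes the best-recovering patients from the heparin arm only. The documents do not support that: patients who leave before the third dose fail in both arms. Only a narrow slice, about Days 5-6, differs. This stands.
- **The direction is not established.** It is tempting to say that the set is biased toward rNAPc2. That requires early leavers to have a better D-dimer change, which neither document shows. Their last sample is taken two to three days before Day 8, so D-dimer has had less time to fall and their change could be smaller. The right-hand column of the second table shows the bias reversing. This stands.
- **Few patients may be affected.** Protocol 5.2, exclusion 6, keeps out patients whose discharge or transfer is expected within 5 days. That limits the share, but it concerns expectation at entry and does not prevent a Day 5-6 discharge.
- **The asymmetry may be deliberate.** Protocol 6.5.1 gives a half-life of about 72 hours for rNAPc2 after the Day 5 dose, against about 4.5 hours for LMWH and 1 hour for UFH, so three doses and heparin through Day 7 might both represent cover up to Day 8. The SAP does not say so. In SAP 11.2, one and two doses are paired with heparin through Days 1 and 3, the dosing days themselves; only the third pairing adds two days. In any case this rationale would not remove selection on length of stay.
- **Outpatient heparin might count.** The SAP does not say. If it did, some Day 5-6 leavers would be restored, but a heparin patient discharged before Day 5 and treated at home through Day 7 would qualify while the rNAPc2 counterpart would not. The asymmetry would move, not disappear.

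**Conclusion.** The asymmetry follows from the text of SAP 5.2, provided heparin as study treatment ends at discharge. It selects on a post-randomization outcome in one arm only and can bias the Per Protocol sensitivity analysis in either direction: toward rNAPc2 if the affected patients have a better D-dimer change, against it if worse.

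The size is conditional. With 10-30% of patients in the gap and a shift of 0.3-0.8 SD, rejection under no effect is about 5% to 21%, against a nominal 5%. The low end is no material inflation, and at zero shift there is none. The share, the SD and the shift are all assumptions.

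A reader might take these percentages as the trial's type I error. They are not. The primary analysis is the between-group rank sum test in the ITT population (SAP Sections 7 and 7.1.1), which this rule does not touch, and the mITT set does not share the feature. The consequence is confined to Per Protocol analyses and summaries. The definition should be corrected, but the primary conclusion does not depend on it.

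**What to change.** Use one landmark for both arms in SAP 5.2. Suggested wording:

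*Received assigned study treatment through the Day 5 visit (all three rNAPc2 doses, or SoC heparin through the Day 5 visit). Discharge after the Day 5 visit does not exclude a participant in either arm.*

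Discharge before the landmark then excludes in both arms and discharge after it in neither. Tying the rule to the visit rather than the calendar day absorbs the one-day window. Capping the heparin requirement at discharge, and leaving rNAPc2 at three doses, would not work: heparin patients who leave before Day 5 would qualify and their rNAPc2 counterparts would not.

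State also whether heparin given after discharge counts toward the criterion. If it counted before the landmark, the same imbalance would return. Bring protocol 9.3 and the three-dose/Day 7 pairing in SAP 11.2 into line, and record the change in SAP Section 12, which does not now list the Per Protocol definition among its differences from the protocol.

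The cost is wording. No dosing, visit, sample or data collection changes, because dose dates and discharge dates are already recorded.
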